#### ***14.2.5.6. Evolution of echocardiographic parameters***

The following echocardiographic parameters were assessed: Left atrial diameter (mm), LAA ( $\text{cm}^2$ ), Left atrial volume (ml), Left atrial volume/BSA ( $\text{ml}/\text{m}^2$ ), LVEF (%), Left ventricular end diastolic volume/BSA ( $\text{ml}/\text{m}^2$ ), Left ventricular end systolic volume/BSA ( $\text{ml}/\text{m}^2$ ), Left ventricular end diastolic diameter (mm), Left ventricular end diastolic volume (ml), Left ventricular end systolic diameter (mm) and Left ventricular end systolic volume (ml).

The echocardiographic parameters values will be described at each time (V1, V2, V4, V6 and V9) and changes described from V4 to last value (V9) and from V2 to last value (V9).

## 15. COMPLIANCE

Estimation of compliance will be presented by treatment group on the Full Analysis Set. The analysis of compliance will be purely descriptive.

Only the global compliance (*ie for the whole duration of study*) will be estimated.

Trial drug compliance will be evaluated, for each patient, by treatment group, by calculating: (estimated number of tablets actually taken divided by theoretical number of tablets to be taken) x 100 (rounded at 1 digit).

The number of tablets actually taken during the study will be estimated as: number of tablets delivered minus number of tablets returned.

In case of trial drug boxes not returned or partially brought back, trial drug compliance will be considered unknown and missing.

The theoretical number of tablets to be taken will be calculated taking into account the actual number of days between dates of visits V2 and V9 considering the daily dose stable

Compliance will be tabulated using continuous scale and according to a 3-scale as: < 80, [80 – 100], and > 100 %.

An extrapolation of the compliance will be also calculated considering the not returned blisters as taken.

## 16. BIOMARKER ANALYSIS

### 16.1. RED BLOOD CELL CONCENTRATIONS OF DHA

Values and changes from baseline for red blood cell concentration of DHA will be performed by treatment group and assessment time on the FAS.

## 17. SAFETY ANALYSIS

The safety analysis will be presented on the Safety Set and will be descriptive.

Baseline Measures: The baseline will be the last value measured before the first intake of study drug. In particular, in case of retest, this retest will be used.

Values measured the same day as the first intake will be considered before the first intake of study drug (planned in the evening with dinner).

Results of retests performed post-trial drug administration will not be analyzed and tabulated (except in case of missing value for technical problem). They will only be displayed in individual data listings.

## 17.1. EXTENT OF EXPOSURE

Extent of exposure to the trial drug expressed in days will be tabulated as quantitative data, by treatment group and globally.

Extent of exposure to the trial drug is defined as the time interval between the actual date of first trial drug administration (*included*) and the actual date of last trial drug administration (*included*), *i.e.*, as the quantity "date of last trial drug administration – date of first trial drug administration + 1 day". (*Incomplete or unknown dates of first and last trial drug applications will be substituted as detailed in section 10.3*).

## 17.2. ADVERSE EVENTS

Any adverse event having been reported during the study for a given subject/patient will be classified using the MedDRA terminology on the Safety Set.

Any recorded AE will be regarded as Treatment Emergent (TE AE) if it occurs or worsens after the first administration (*included*) of the study drug.

The occurrence of an adverse event will be defined by the appearance of a new single event, the reappearance of a previously recovered event or the worsening of a persistent event (relative to its previous status).

If the severity is missing, a severity of "severe" will be assigned.

Missing or incomplete dates will be imputed for the calculation of TEAE as described in section 10.3, but will be presented as reported in the eCRF in the data listings.

A summary table will be produced giving the number (and percentage for patient) of:

- Patients with at least one AE
- Patients with at least one TE AE
- Patients with at least one related TEAE (*i.e.* relationship to the study drug other than "Not suspected")
- Patients with at least one AE leading to definitive study drug discontinuation
- Patients with at least one Serious AE (SAE)
- Occurrences of AEs
- Occurrences of TEAEs

- Occurrences of related TE AEs
- Occurrences of AEs leading to definitive study drug discontinuation
- Occurrences of SAEs

The number and percentage of patients with at least one AE occurred before first administration will be tabulated by MedDRA System Organ Class (SOC), Preferred Term (PT) and Treatment Group.

Numbers and percentages of subjects with at least one reported treatment emergent adverse event will be tabulated by treatment group (by decreasing order of frequency in the verum group). and:

- By system organ class and preferred term
- By system organ class, preferred term, and the most severe intensity
- And by system organ class, preferred term and the most severe relationship to the study drug.

"The number and percentage of patients with at least one drug related TE AE (i.e. relationship to the study drug other than "Not suspected") will be tabulated by SOC, Preferred Term and Treatment group in decreasing order for the treatment group (by decreasing order of frequency in the verum group).

The number and percentage of patients with at least one TEAE, and the number of occurrences of TEAEs, will be tabulated by MedDRA SOC, Preferred Term, seriousness and Treatment Group (by decreasing order of frequency in the verum group).

The number and percentage of patients with at least one related TEAE, and the number of occurrences of related TEAEs, will be tabulated by MedDRA SOC, Preferred Term, seriousness and Treatment Group (by decreasing order of frequency in the verum group).

### **Serious Adverse Events (SAEs)**

Serious adverse events will also be described on an individual basis: treatment group, patient's code, sex and age, investigator's reported term, preferred term, date of onset according to the date of the first study treatment administration, duration, action taken regarding the study treatment administration, use of a corrective treatment, outcome and relationship to the study treatment in the investigator's opinion.

### **AEs leading to the definitive discontinuation**

All AEs having led to the definitive discontinuation of the trial drug will be listed and exhaustively described, on an individual basis, by treatment group, in exactly the same way as serious adverse events previously described, during the study (from the date of the first trial drug intake onwards).

**Deaths**

Deaths will be also listed and exhaustively described, on an individual basis.

All AEs will be included in the listings of individual data.

### 17.3. VITAL SIGNS

Descriptive statistics over time of values and changes from baseline of supine Systolic Blood Pressure (SBP mmHg), Diastolic Blood Pressure (DBP mmHg) and Heart Rate (HR bpm) will be tabulated by treatment group and assessment time.

Figures: mean changes and standard error of mean (SEM) will be represented graphically from baseline over time.

The scales of vertical axis will be:

SBP mmHg	DBP mmHg	HR bpm
From -15 to +15	From -10 to +10	From -15 to +15

**PSC and PSCV for supine parameters**

The number and percentage of patients with at least one Predefined Potentially Clinically Significant Change (PSC) and with at least one PSC Leading to Clinically Significant Value (PSCV) will be tabulated by treatment group (cf Appendix 2, Table 1).

### **Orthostatic Hypotension**

The number and percentage of patients experiencing at least one post-baseline orthostatic hypotension (cf Appendix 2, Table 2) will be tabulated by treatment group. Vital signs not measured according to protocol were identified during data review meeting. Measures performed first in standing position and then in supine position will not be taken into account for the analysis of orthostatic hypotension.

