## 18. CHANGES SINCE PROTOCOL REDACTION

The following modifications were made to statistical analyses compared to those envisaged in the Version 9 of the protocol dated December 6th, 2016:

- predictive probability of success and conditional power for primary efficacy criterion will be added
- subgroups analyses for primary criterion will be added
- ROC curves for primary criterion exploratory analyses according to DHA will be added
- the secondary criteria analyses repeated on the PP set will not be performed
- the secondary criteria were extended to the flutter detection as the primary efficacy criterion
- VS parameters in standing positions will not be analysed (only provided in individual data listings)
- Frequencies on the ECG clinical interpretation will not be presented (not collected)- Analysis of TEAEs occurrences by MedDRA SOC, PT, seriousness and Treatment Group will be added as per EudraCT requirement

**Note:** the Full Analysis Set definition was clarified with the definition of successful cardioversion as either spontaneous cardioversion before V3 or successful ECV performed at V3.

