**Table 2: Definition of orthostatic hypotension**

Orthostatic Hypotension *
SBP Decrease $\geq 20$ mmHg or DBP Decrease $\geq 10$ mmHg between supine and standing positions

The Consensus Committee of the American Autonomic Society and the American Academy of Neurology. Consensus statement on the definition of orthostatic hypotension, pure autonomic failure and multiple system atrophy. Neurology 1996;46:1470-3.

Appendix 3 LIST OF PREDEFINED POTENTIALLY CLINICALLY SIGNIFICANT CHANGE FOR LABORATORY VALUES(c)	page 1/1
--	-----------------

PARAMETERS	UNIT	PSC	
		Decrease	Increase
MUSCLE	Creatine Phosphokinase	U / l	- 236
KIDNEY	Creatinine	µmol/l	- 35
	Urea	mmol/l	- 3.2
	Uric acid	µmol/l	- 119
	Phosphate	mmol/l	0.39 0.39
	Calcium	mmol/l	0.30 0.30
ELECTROLYTES	Sodium	mmol/l	8 8
	Potassium	mmol/l	1.1 1.1
	Chloride	mmol/l	8 7
	Bicarbonate	mmol/l	7 8
METABOLISM/ NUTRITIONAL	Glucose (random)	mmol/l	3 3.7
	Albumin	g/l	6 6
	Protein	g/l	11 10
	Cholesterol	mmol/l	- 1.97
	HDL cholesterol	mmol/l	0.91 0.85
	LDL cholesterol	mmol/l	2.17 2.04
	Triglycerides	mmol/l	- 2.91
ERYTHROCYTES	Erythrocyte count	T/l	0.7 0.7
	Haemoglobin	g/l	20 -
	Haematocrit	1	0.06 0.06
	MCV	fl	7 7
	MCH (Fe)	fmol	0.19 0.19
	MCHC (Fe)	mmol/l	2 2
LEUKOCYTES	Leukocyte count	G/l	4.2 3.8
DIFFERENTIAL COUNT	Neutrophils	G/l	3.47 3.19
	Lymphocytes	G/l	1.76 1.63
	Monocytes	G/l	- 0.49
	Eosinophils	G/l	- 0.41
	Basophils	G/l	- 0.14
URINE	Specific gravity	-	0.017 0.015
	pH	-	2 2
LIVER	Total bilirubin	µmol/l	- 10
	ASAT (SGOT)	U/l	- N x (23/36)
	ALAT (SGPT)	U/l	- N x (28/45)
	Gamma GT	U/l	- N x (25/38)
	Alkaline phosphatase	U/l	-- N x (30/95)

N = upper limit of normal range

(c) Delta-limits from « Routine Laboratory Tests in Clinical Trials » W. Leigh Thompson, Rocco L. Brunelle, Gregory G. Enas, Patrick J. Simpson and Randy L. Walker Lilly Research Laboratories, Lilly Corporate Center, Indianapolis, Indiana in « Clinical Trials and Tribulations » 1988.

Appendix 4 DEFINITION OF CLINICALLY NOTEWORTHY ABNORMAL LABORATORY VALUES (CNALV)	page 1/1
--	-----------------

PARAMETERS	Baseline value	CNALV
HAEMOGLOBIN	Not missing	Decrease of at least 2g/dl and value < 10 g/dl
	Missing	Value <10g/dl
NEUTROPHILS	-	< 1 500/mm 
WBC (if missing value for neutrophils)	-	< 3 000/mm 
PLATELETS	-	< 100 000/mm 

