12.4.2.3	CNALV: Patients with ALAT > 2N or ASAT > 2N or ALP > 1.25N or TB > 1.5N, and normal baseline value, or GGT > 3 N (if baseline<3N) [Safety Set]	12_4_2_3d_liver.RTF
12.4.2.3	CNALV: Patients with creatinine > 150 µmol/L and increase by 30% from baseline value (if any) [Safety Set]	12_4_2_3e_creat.RTF
12.4.2.3	Patients with estimated creatinine clearance < 30 ml/min [Safety Set]	12_4_2_3f_clear.RTF
12.5.1	SBP Changes over Time [Safety Set]	12_5_1_1_figCH_SBP.gif
12.5.1	DBP Changes over Time [Safety Set]	12_5_1_1_figCH_DBP.gif
12.5.1	HR Changes over Time [Safety Set]	12_5_1_1_figCH_HR.gif
12.5.1	Supine VS measurements : Incidence of post-baseline PSCs and PSCVs [Safety Set]	12_5_1_2_SCVS.RTF
12.5.1	Supine BP measurements : Incidence of post-baseline PSCs and PSCVs [Safety Set]	12_5_1_2_SCBP.RTF
12.5.1	Supine HR measurements : Incidence of post-baseline PSCs and PSCVs [Safety Set]	12_5_1_2_SCHR.RTF
12.5.1	BP measurements : Number of patients with at least one post-baseline orthostatic hypotension [Safety Set]	12_5_1_2_OrthoBP.RTF
12.5.3	Patients with ECG abnormalities (Investigator's evaluation) [Safety Set]	12_5_3_1_2_ecg_abn.RTF
14.1	Number of patients per country and centre [Randomised patients]	14_1a_asetpercenter_all.RTF
14.1	Number of patients with minor deviations [Randomised Patients Set]	14_1b_minor_dev.RTF
14.1	Demographic characteristics [Safety Set]	14_1c_demoSaf.RTF
14.1	Demographic characteristics [PP]	14_1c_demoPP.RTF
14.1	Disease characteristics at baseline [PP]	14_1c_discharPP.RTF
14.1	Number (%) of patients with at least one medical or surgical history by MedDRA primary system organ class and preferred term [Safety Set]	14_1d_medhist_socpt_saf.RTF
14.1	Number (%) of patients with at least one concomitant disease at time of selection by MedDRA primary system organ class and preferred term [Safety Set]	14_1e_cdiseasesel_socpt_saf.RTF
14.1	Number (%) of patients with at least one medication taken before first study drug administration, by WHO-Drug ATC1and ATC2 [Safety Set]	14_1f_pmed_atc_saf.RTF
14.1	Number (%) of patients with at least one medication before first study treatment administration linked to the study pathology, by WHO-Drug ATC1and ATC2 [Safety Set]	14_1g_pmed_link_atc_saf.RTF
14.3.1	Number of patients with at least one AE occurred before first administration by MedDRA primary system organ class and preferred term [Safety Set]	14_3_1_ae_socpt.RTF

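### Orthostatic hypotension is counted at any post-baseline visit without regard to baseline status, so one descriptive safety count mixes new and pre-existing cases

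*SAP*

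**What the plan says.** Under the Orthostatic Hypotension heading in section 17.3 the SAP plans this output: "The number and percentage of patients experiencing at least one post-baseline orthostatic hypotension (cf Appendix 2, Table 2) will be tabulated by treatment group". Appendix 2, Table 2 defines a case as a fall of at least 20 mmHg systolic or 10 mmHg diastolic "between supine and standing positions". Appendix 5 lists the matching table, 12_5_1_2_OrthoBP: "BP measurements : Number of patients with at least one post-baseline orthostatic hypotension [Safety Set". None of the three places mentions orthostatic status before the first dose.

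Two neighbouring rules do refer to baseline:

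- **Supine vital signs (section 17.3).** The planned count is: "The number and percentage of patients with at least one Predefined Potentially Clinically Significant Change (PSC", together with PSCV. In Appendix 2, Table 1 a PSC is an increase or decrease of a set size. A PSCV is a threshold value plus such a change.
- **Adverse events (section 17.2).** An event is treatment-emergent "if it occurs or worsens after the first administration" of study drug.

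On standing readings, section 17.3 sets an order rule: "Measures performed first in standing position and then in supine position will not be taken into account for the analysis of orthostatic hypotension". Section 18 says: "VS parameters in standing positions will not be analysed (only provided in individual data listings". On status, section 17 says: "The safety analysis will be presented on the Safety Set and will be descriptive".

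**The concern.** A table of post-baseline orthostatic hypotension by arm will be read as a sign of what the drug does to postural blood pressure. As specified, it answers a different question: how many patients had at least one qualifying fall after dosing, whether or not they had one before.

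This has two consequences. First, patients with the condition at baseline who are flagged again add to the count in both arms and carry little information about the drug, so the contrast is attenuated. Second, if the arms differ at baseline by chance, the difference passes straight into the post-baseline count, in either direction. No planned table shows baseline orthostatic status, so the reader of the tables could not tell.

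**Working it through.** **Inputs.** The SAP gives no orthostatic hypotension rate at baseline or afterwards, so there is no figure of its own to reproduce on this point. All rates below are assumptions. From the SAP come only the counting rule (section 17.3), the definition (Appendix 2, Table 2) and the 135 randomised patients (section 6, Sample size).

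**Formula.** Let p be the baseline prevalence (equal in both arms), r the probability that a prevalent case is flagged again after baseline (equal in both arms), and c and t the new-onset risks on placebo and active among patients free of it at baseline.

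- Tabulated risk, placebo: p·r + (1−p)·c
- Tabulated risk, active: p·r + (1−p)·t
- Tabulated difference: (1−p)·(t−c), whatever the value of r

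**Main illustration.** c = 15%, t = 25%, r = 100%. Among patients free of it at baseline the difference is 10 points and the ratio 0.25/0.15 = 1.67.

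| p | Placebo | Active | Difference (points) | Ratio |
|---|---|---|---|---|
| 10% | 0.10 + 0.90×0.15 = 0.235 | 0.10 + 0.90×0.25 = 0.325 | 9.0 | 1.38 |
| 15% | 0.15 + 0.85×0.15 = 0.2775 | 0.15 + 0.85×0.25 = 0.3625 | 8.5 | 1.31 |
| 25% | 0.25 + 0.75×0.15 = 0.3625 | 0.25 + 0.75×0.25 = 0.4375 | 7.5 | 1.21 |

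**Sensitivity to the assumed rates.** c = 5%, t = 15%, r from 70% to 100%. Among patients free of it at baseline the difference is 10 points and the ratio 3.0.

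| p | Difference (points) | Ratio at r = 70% | Ratio at r = 100% |
|---|---|---|---|
| 10% | 9 | 1.78 | 1.62 |
| 20% | 8 | 1.44 | 1.33 |
| 30% | 7 | 1.29 | 1.21 |

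The direction is the same in every case. The size depends on the assumed rates, and the ratio moves far more than the difference.

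**Chance imbalance at baseline.** With an even split (an assumption) there are about 67 patients per arm. At an assumed prevalence of 15%, the standard error of the between-arm difference in prevalence is √(2 × 0.15 × 0.85 / 67) = 0.062, or about 6 points. That is of the same order as the differences in the first table.

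**Denominator of a baseline-free row.** At p = 25%, about 0.25 × 67 ≈ 17 patients per arm leave the row and about 50 remain. At p = 10%, about 7 leave and 60 remain.

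**The case against.** **The count is clear, and baseline-free flags occur elsewhere.** The rule is reproducible. Appendix 4 sets no baseline condition for neutrophils, white cells or platelets, and the creatinine clearance listing below 30 ml/min has none either. This stands: the SAP has no uniform convention that the rule breaks. The contrast is with the other vital-sign flags in the same section and with treatment-emergent adverse events.

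**The harm is measured on a scale that the SAP does not plan.** The table shows numbers and percentages, with no risk ratio and no test. This also stands. The percentage-point difference is the fairer measure, and it shrinks only by the factor 1−p.

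**The information is not lost.** Vital signs are listed individually (16.2.9.1), and orthostatic hypotension reported as an adverse event that starts or worsens on treatment is counted in section 17.2. This stands in part. A reader would still have to rebuild baseline status patient by patient.

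**A stronger reading that does not hold.** A reader might infer from section 18 that standing values are withdrawn from all analysis, so that the orthostatic table is cancelled. The document does not support that. Section 17.3 summarises supine pressure and heart rate, so the section 18 bullet reads naturally as saying that standing values get no summaries of their own. The orthostatic count is explicitly planned and has its own rule on measurement order, its own definition and a named output. What remains is loose wording.

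**Conclusion.** The point holds as a minor reporting weakness. Section 17.3 does not separate new from pre-existing orthostatic hypotension, and no planned table shows baseline status.

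Only the direction of the attenuation is established, and it rests on equal prevalence and equal re-flagging in both arms. In the main illustration the loss is 1.0 to 2.5 percentage points out of 10. All of those rates are assumed, and the SAP does not show that baseline prevalence in this population is large. A reader might infer that the table would hide a real drug effect. That cannot be concluded either: the safety analysis is descriptive, no decision rule depends on the count, and the primary efficacy comparison is untouched.

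**What to change.** 1. In section 17.3 and table 12_5_1_2_OrthoBP, keep the all-patient count and add a split by baseline orthostatic status: yes, no, missing. Show the incidence among patients without it at baseline. Derive baseline status with the section 17 baseline definition and the same rule on measurement order.
2. In section 18, state that standing values are not summarised on their own but are used to derive orthostatic hypotension.

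The cost is a row split in an existing table and one sentence. No new data are needed beyond baseline standing readings where they were recorded; the missing row covers the rest. The baseline-free row has a smaller denominator, by about 17 patients per arm at an assumed 25% prevalence, which is why it should sit beside the all-patient count and not replace it.

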### 17.4. LABORATORY DATA

Clinically noteworthy abnormal laboratory values (CNALV) (See Appendix 4) will be identified and described on an individual basis. Five separate individual data listings by treatment group will be provided:

- for haemoglobin (including corresponding individual results of erythrocytes and haematocrit),
- for platelets (including corresponding individual results of erythrocytes and leucocytes),
- for liver function parameters (including corresponding individual results of gamma-GT),

- for neutrophils or leucocytes (including corresponding individual results of basophils, eosinophils, lymphocytes and monocytes)
- for serum creatinine

Estimated creatinine clearance (ml/min) will be calculated using Cockcroft and Gault method as

$$\frac{[140 - \text{age (in years)}] \times \text{body weight (in kg)}}{\text{serum creatinine (in } \mu\text{mol/L}) \times 0.814} \times (0.85 \text{ for female})$$

Patients with estimated creatinine clearance (Cockcroft method)  $< 30$  ml/min will be also described on an individual basis. Values of estimated creatinine clearance (Cockcroft method) will be classified as following:

Creatinine clearance categories (ml/min)
<15
[15-30[

For each laboratory parameter, values and changes from baseline will be tabulated by treatment group and assessment time.

For all biochemistry parameters, scatter plots highlighting individual results will display the baseline and last value of the laboratory measurements for each patient by locating the point defined by the baseline value on the abscissa and respectively last value in the ordinate.

For all haematology parameters, scatter plots highlighting individual results will display the baseline and week 4, week 12 and week 24 of the laboratory measurements for each patient by locating the point defined by the baseline value on the abscissa and respectively week 4, week 12 and week 24 value in the ordinate.

Each treatment group will be differently identified. The first bisecting line ( $45^\circ$  line), the lines of lower and upper normal range, the lines of Potentially Clinically Significant Change (PSC) range and Clinically noteworthy abnormal laboratory value (CNALV) range added on the plots (see Appendices 3 and 4).

For all blood laboratory parameters, shift tables will be provided to depict the numbers of patients with post-trial drug administration variations at each assessment time as compared to the baseline

values (measured on the last blood sample collected before the first trial drug administration) by treatment group. A 3-point scale (low, normal, high) will be used as defined by the normal ranges in use in the laboratory in charge of the assays.

*Note:* zero laboratory values without clinical significance will have to be considered as missing for statistical analysis.

